2 OBJECTIVES

2.1 Primary Objectives

To describe the characteristics of European patients newly prescribed dapagliflozin by age, sex, dapagliflozin dose, country, selected co-morbidities, and selected concomitant medications.

The proposed drug utilization study will specifically describe dapagliflozin use among all new dapagliflozin users including dapagliflozin users in the following subgroups (separate analysis for each subgroup):

- patients > 75 years-old,
- combination use with loop diuretics or pioglitazone,
- patients with a known history of moderate or severe renal impairment and in kidney failure,
- patients not reported to have T2DM.

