3.2.1 Inclusion Criteria

- 1) Enrolled in the Cegedim databases for at least one year prior to the first prescription of dapagliflozin (baseline time period),
- 2) All patients identified in the database who newly received at least one dapagliflozin prescription during the study period.

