3.3.2 Content of the Cegedim LPDs for T2DM patients

Table 3.3.2-1 gives approximate estimates of the proportion of T2DM patients captured using the Cegedim LPD in each country.

The total number of T2DM patients in the respective countries during the same period is not known, but may be roughly estimated based on information from the Diabetes Atlas 2012¹ and assuming that this population represents approximately 90 % of the total diabetic population.

Table 3.3.2-1: Estimates of the proportion of T2DM patients captured in Cegedim LPDs (year 2012)

	Source	France	Germany	Italy	Spain	Belgium	UK
Diabetic Population (in thousands)	Diabetes Atlas http://www.idf.org/diabetesatlas	3,493	5,249	3,903	3,249	547	3,336
Estimates of T2DM patients Total Population (in thousands)	0.9 x Diabetic population	3,115	4,724	3,523	2,925	493	3,002
T2DM patients in CegedimLPD s (in thousands)	Cegedim LPD	65	37	42	14	13	118
% of T2DM population in Cegedim LPDs:	T2DM patients in Cegedim LPDs/Estimates of T2DM patients Total Population	2.1%	0.8%	1.2%	0.5%	2.6%	3.9%

Date: 13-Nov-2013

Key metrics for the T2DM patients in GP's LPDs are provided for each country in Table 3.3.2-2.

Information collected during the course of one year (2012), on serum creatinine and eGFR for T2DM patients is detailed in Table 3.3.2-3.

These data, when insufficiently documented in the course of one year, can be extracted over an extended period of time (two years) in patients' medical record in order to add information and increase possibilities for meaningful analyses.

In addition, this information can be complemented in each country by a search of patient's medical records with a list of diagnostic codes identifying chronic kidney disease, renal failure, end-stage renal disease and related diagnoses (according to Wan J. et al² and Denburg M.R., et al³.)

Table 3.3.2-2: Key Data Metrics of T2DM Patients in GP's LPDs

	France	ITALY	UK	GERMANY	SPAIN	BELGIUM
GENERAL DATA						
Number of patients having visited a physician	100,00%	100,00%	100,00%	100,00%	100,00%	100,00%
Of which Male	58,0%	51,9%	55,2%	51,8%	53,8%	53,4%
Female	42,0%	48,1%	44,8%	48,2%	46,2%	46,6%
BIOMETRIC DATA	19					
Number of patients with a weight recorded (1 year history)	56,0%	39,9%	83,5%	29,1%	28,3%	37,3%
Number of patients with height recorded (1 year history)	20,6%	39,6%	30,8%	28,3%	23,2%	13,9%
Number of patients with BMI recorded (1 year history)	20,2%	39,4%	29,0%	28,2%	20,7%	13,2%

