3.4.1 Outcomes/Endpoint Variables

Table 3.4.1-1 includes the characteristics and definitions of how dapagliflozin users will be categorized and described.

Table 3.4.1-1: Categorization of Dapagliflozin Users

Characteristic	Definition
Patient Demographics, at initiation of dapagliflozin use:	
Age categories	< 45, 45-59, 60-74, >= 75
Sex	Male or Female
Country	Belgium, France, Germany, Italy, Spain, United Kingdom
Concomitant medications before, at initiation of and	Loop diuretics (ATC code C03Cx)
during dapagliflozin use 1	Pioglitazone (Actos, Glustin) (ATC code A10BG),
	Biguanides (ATC Code A10BA)
	Sulfonamide derivates (ATC code A10BB and A10BC)
	Dipeptidyl peptidase 4 inhibitors (DDP4) (ATC code A10BH)
	Glucagon-like peptide 1 (GLP-1, exenatide, liraglutide, ATC code A10BX),
	Alpha glucosidase inhibitors (ATC code A10BF).
	Insulin (ATC code A10A)
Concomitant co-morbidities, at initiation of dapagliflozin use:	
Baseline history of moderate renal impairment	CrCl or eGFR ² value between 30-60 within 12 months prior to the dapagliflozin dispensing
Baseline history of severe renal impairment	CrCl or eGFR value < 30 within 12 months prior to the dapagliflozin dispensing
Baseline history of renal failure	Diagnosis codes for end stage renal disease or dialysis (see Appendix 3)
Congestive heart failure	Diagnosis codes for congestive heart failure (see Appendix 3)
Hypertension	Diagnosis codes for hypertension (see Appendix 3)
Type 2 Diabetes Mellitus, at initiation of dapagliflozin use:	Diagnostic code for T2DM within 12 months prior to the dapagliflozin dispensing (see Appendix 3) OR
	Prescription for an antiglycemic medication within 12 months prior to the dapagliflozin dispensing

Table 3.4.1-1: Categorization of Dapagliflozin Users

Characteristic	Definition
Dapagliflozin Dose, at initiation of dapagliflozin	10 mg
use:	5 mg
Off-Label Use	Patients meeting one of the following criteria:
	 17 years old or younger on index date
	• 75 years of age or older on index date
	 No diagnostic codes for Type 2 Diabetes Mellitus, at or before the initiation of dapagliflozin use (see definition above)
	• Baseline history of moderate renal impairment (see definition above)
	• Baseline history of severe renal impairment (see definition above)
	• Baseline history of renal failure (see definition above)

^[1] Pioglitazone sales are suspended in France and Germany

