APPENDIX 3 CODE LISTS

	ICD9	ICD10
T2DM	250.x0	E10.x
Acute renal failure	584.x	N17.x
Severe chronic renal failure	585.x	N18.3, N18.4, N18.5
U failure	586.x	N19.
Dialysis	V45.11, V56.x	Y84.1
Renal transplantation	E878.0	Y83.0
Congestive heart failure	428.0	150.0
Hypertension	401.x	I10.x, I11.x, I12.x, I13.x, I15.x

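### Moderate and severe renal impairment are counted only from a 12-month laboratory value, so coded CKD and the section 3.3.2 look-back options have no defined role

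*Protocol*

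**What the plan says.** Section 2.1 sets the target group as "patients with a known history of moderate or severe renal impairment and in kidney failure". Research question 2 (section 1.2) asks for the proportion with moderate to severe impairment among all patients prescribed the drug.

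Table 3.4.1-1 (section 3.4.1) turns this into three rows:

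- Moderate: a CrCl or eGFR "value between 30-60 within 12 months prior to the dapagliflozin dispensing".
- Severe: "CrCl or eGFR value < 30 within 12 months prior to the dapagliflozin dispensing".
- Renal failure: "Diagnosis codes for end stage renal disease or dialysis (see Appendix 3".

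The off-label definition in the same table takes over all three rows by reference.

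Section 3.3.2 says of creatinine and eGFR data that these, "when insufficiently documented in the course of one year, can be extracted over an extended period of time (two years", and that "this information can be complemented in each country by a search of patient's medical records with a list of diagnostic codes identifying chronic kidney disease" and related diagnoses. Neither option appears in Table 3.4.1-1, in the 12-month baseline period of the synopsis, or in the inclusion criterion, which asks only that patients be "Enrolled in the Cegedim databases for at least one year prior to the first prescription of dapagliflozin".

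Appendix 3 lists ICD-9 585.x and ICD-10 "N18.3, N18.4, N18.5" under a heading for severe chronic renal failure. No row of Table 3.4.1-1 bears that name, and no Appendix 3 row is named for end-stage disease.

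**The concern.** The objective speaks of known history, but the two rows that carry it recognise only a recent measurement. A diagnosis that the GP has already recorded does not bring a patient into either row. Such a patient is lost from the numerator of research question 2 and kept in its denominator, so the proportion is understated by an amount that the report could not show.

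The renal off-label criteria inherit the problem. Whether a coded patient is off-label on renal grounds depends on whether the renal-failure row is read by its label or by the code list it cites.

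The two-year option has no threshold for when data are too sparse and no statement that it applies to all countries alike. If it were used for some countries only, part of any between-country difference would reflect the length of look-back. As one year of enrolment is enough for inclusion, the second year also exists for only some patients.

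**Working it through.** **Two example records against the text**

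| Record | Moderate/severe rows | Renal-failure row | Section 3.3.2 options |
|---|---|---|---|
| A: code N18.4, no value in 12 months | Not counted | No by the row's label; yes if the Appendix 3 list is applied as cited | Found by the code search, but no row is assigned |
| B: eGFR 45, 15 months before index, no code | Not counted | No | Moderate under the two-year option |

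The protocol supports two answers for each record.

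**One-year availability of any eGFR**

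The inputs are the counts in Table 3.3.2-3 (T2DM patients, 2012). The formula is p = patients with an eGFR recorded or calculated / T2DM patients.

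| Country | Count | p | Printed |
|---|---|---|---|
| UK | 93,300 / 118,000 | 79.1% | 79% |
| Germany | 19,300 / 37,000 | 52.2% | 52% |
| Italy | 20,850 / 42,000 | 49.6% | 50% |
| Spain | 4,200 / 14,000 | 30.0% | 30% |
| France | 12,300 / 65,000 | 18.9% | 20% |
| Belgium | 1,100 / 13,000 | 8.5% | 9% |

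The printed figures reproduce, apart from small differences for France and Belgium that do not matter here. Pooled: 151,050 / 289,000 = 52.3%, so 47.7% have no eGFR in one year.

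**Adding a second year**

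The protocol gives no two-year figure. I assume that the earlier year has the same p. Then:

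- lower limit (the same patients tested each year): p, no gain;
- independent years: 1 − (1 − p)²;
- strict upper limit (as little overlap as possible): min(1, 2p).

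For the two databases on which section 4.1.1.1 mainly rests the renal analyses:

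- UK: 1 − 0.209² = 95.6%, which is 1.21 times 79.1%; range 79.1% to 100%.
- Germany: 1 − 0.478² = 77.1%, which is 1.48 times 52.2%; range 52.2% to 100%.

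The window alone can therefore shift availability by different amounts in these two databases.

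**Limits of this arithmetic**

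The table counts patients with any eGFR, not with one below 60, and describes T2DM patients in 2012, not dapagliflozin initiators. A note in section 3.3.1 on investigations unavailable in Germany could be read to include laboratory tests; I have taken the German counts at face value. The number with a CKD code and no value is not given, so the effect of leaving out codes cannot be computed.

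**The case against.** The strongest reply is that section 3.3.2 only describes what the databases allow. Its verbs are permissive, and the code search is offered for each country. The operative rule is a single 12-month window, consistent across Table 3.4.1-1, the synopsis and section 5.2. Section 3.3.1 leaves harmonised diagnosis algorithms to the SAP, which is not shown. The databases that matter most are the UK and Germany. Section 1.1 expects no French users and reports no reimbursement in Belgium, so the countries with the sparsest data may contribute little.

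Much of this stands. A reader might infer that coded CKD patients are classed as unimpaired. The protocol does not say so: it has no such category, it reports missing data without imputing (section 4.1), it describes patients with and without eGFR (section 4.1.1.1), and it calls renal function uncertain without a recent creatinine (section 5.1). A reader might also infer that look-back will differ by country. The text only leaves that open. Nor can one say that a stage 4 code falls outside renal failure, since the cited list contains it.

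What the reply does not remove is the conflict inside the protocol. The SAP may define algorithms, but the protocol itself fixes a value-only definition, mentions other sources for the same variable, and cites a code list that does not match its row. Reporting missing values does not bring back a patient whose record already states the impairment.

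**Conclusion.** The point holds in a limited form. As written, a patient with a CKD code and no 12-month value is not counted as moderate or severe but remains in the denominator of research question 2. That patient's place in renal failure and off-label use is undetermined. Differing look-back is a possibility that section 3.3.2 leaves open, not a stated rule.

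The number of patients affected cannot be derived. What can be shown is the room for it: about 21% of UK and 48% of German T2DM patients have no eGFR in a year. A second year might remove none of that gap, all of it, or, if years are independent, bring availability to 95.6% and 77.1%. This rests on 2012 T2DM patients and an equal testing share in both years.

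It should be corrected because it concerns a key variable of a study done at regulatory request, and the data needed are already among those to be extracted.

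**What to change.** Reconcile section 3.3.2, Table 3.4.1-1 and Appendix 3:

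- Keep the 12-month value as one rule for all countries.
- Add a pre-stated known-history definition: a qualifying 12-month value, or a listed CKD code at or before index, with stage used only where the coding system gives it.
- Report by country: value only, code only, either, and renal function unknown (no value and no code).
- State which Appendix 3 codes feed which row, and align the renal-failure label with its list.
- Allow a 24-month look-back only as a labelled sensitivity analysis, applied alike in all countries to patients with at least 24 months of enrolment.

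The cost is protocol wording, extra table columns and some work on codes. Appendix 3 has 585.x undivided and three N18 stages under one heading, and it gives no Read codes, which the UK database uses. A coded stage is less precise than a value; separate columns keep that visible. The 24-month restriction can be expected to remove many German patients, where median database follow-up is 27 months (section 3.3.1) against 117 in the UK, and the report should say so.

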Page: 1

Protocol Number: MB102134

Date: 13-Nov-2013

Observational Study Protocol MB102134

OBSERVATIONAL SINGLE-COHORT DATA BASE STUDY OF DAPAGLIFLOZIN UTILISATION IN EUROPE

This document is the confidential and proprietary information of Bristol-Myers Squibb Company, its global affiliates (BMS) and AstraZeneca (AZ). By reviewing this document, you agree to keep it confidential and to use and disclose it solely for the purpose of assessing whether your organization will participate in and/or the performance of the proposed BMS/AZ-sponsored study. Any permitted disclosures will be made only on a confidential "need to know" basis within your organization or to your independent ethics committee(s). Any other use, copying, disclosure or dissemination of this information is strictly prohibited unless expressly authorized in writing by BMS/AZ. Any supplemental information (e.g., amendments) that may be added to this document is also confidential and proprietary to BMS/AZ and must be kept in confidence in the same manner as the contents of this document. Any person who receives this document without due authorization from BMS/AZ is requested to return it to BMS/AZ or promptly destroy it. All other rights reserved.

SYNOPSIS

Observational Study Protocol MB102134

Protocol Title: Observational Single-Cohort Data Base Study of Dapagliflozin Utilisation in Europe

Department: Bristol-Myers Squibb Epidemiology and AstraZeneca Global Epidemiology

Objective(s): *Primary objective:* To describe the characteristics of European patients newly prescribed dapagliflozin by age, sex, dapagliflozin dose, country, selected co-morbidities, and selected concomitant medications.

The proposed drug utilization study will specifically describe dapagliflozin use in:

- patients > 75 years-old,
- combination use with loop diuretics or pioglitazone,
- patients with a known history of moderate or severe renal impairment and in kidney failure,
- patients lacking a diagnostic code indicating type 2 diabetes.

Study Design: This is an observational single-cohort data base study with descriptive data analyses among patients receiving dapagliflozin within electronic medical records in Europe. The study will describe the utilization pattern of dapagliflozin during the first 3.5 years after marketing authorization and launch in Europe specifically in Belgium, France, Germany, Italy, Spain and United Kingdom.

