1 INTRODUCTION

Dapagliflozin (BMS-512148) is a highly potent, selective, and reversible inhibitor of the human renal sodium glucose co-transporter (SGLT2), the major transporter responsible for renal glucose reabsorption. Dapagliflozin lowers plasma glucose by inhibiting the renal reabsorption of glucose, and by promoting its urinary excretion making it a member of an emerging therapeutic class in the treatment of type 2 diabetes mellitus (T2DM).

Dapagliflozin is indicated in adults aged 18 years and older with type 2 diabetes mellitus (T2DM) to improve glycaemic control as:

- Monotherapy when diet and exercise alone do not provide adequate glycaemic control in patients for whom metformin is considered inappropriate due to intolerance.
- Add-on combination therapy in combination with other glucose lowering medicinal products including insulin, when these, together with diet and exercise, do not provide adequate glycaemic control.

According to the summary of product characteristics (SmPC), the recommended posology and method of administration are the following:

- The recommended dose is 10 mg dapagliflozin once daily for monotherapy and add-on combination therapy with other glucose lowering medications including insulin. When dapagliflozin is used in combination with insulin or an insulin secretagogue, such as a sulphonylurea, a lower dose of insulin or insulin secretagogue may be considered to reduce the risk of hypoglycaemia.
- Dapagliflozin can be taken orally once daily at any time of day with or without food. Tablets are to be swallowed whole.

The following precautions for use must be taken for the following special populations:

- Renal impairment: The efficacy of dapagliflozin is dependent on renal function, and efficacy is reduced in patients who have moderate renal impairment and likely absent in patients with severe renal impairment. Dapagliflozin is not recommended for use in patients with moderate to severe renal impairment (patients with creatinine clearance [CrCl] < 60 ml/min or estimated glomerular filtration rate [eGFR] < 60 ml/min/1.73 m²). No dosage adjustment is indicated in patients with mild renal impairment.
- Hepatic impairment: No dosage adjustment is necessary for patients with mild or moderate hepatic impairment. In patients with severe hepatic impairment, a starting dose of 5 mg is recommended. If well tolerated, the dose may be increased to 10 mg.

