1.2 Research Question

Research question 1: What are the baseline characteristics of the patients prescribed dapagliflozin in Europe?

Research question 2: What proportion of patients prescribed dapagliflozin have baseline moderate to severe renal impairment?

Research question 3: What proportion of patients prescribed dapagliflozin are 75 years of age or older at the time of the index prescription?

Research question 4: What proportion of patients prescribed dapagliflozin are also users of loop diuretics or pioglitazone during the baseline period and the available follow-up period?

Research Question 5: What proportion of patients prescribed dapagliflozin does not have a diagnosis of Type II Diabetes during the baseline period or on the index date?

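### Type 2 diabetes is defined by code or prescription in one place and by code or diagnosis alone in others, over different windows, so use outside T2DM has no single computable answer

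*Protocol*

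**What the plan says.** The protocol describes the group without T2DM in five places.

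- **Table 3.4.1-1, T2DM row (section 3.4.1).** First limb: "Diagnostic code for T2DM within 12 months prior to the dapagliflozin dispensing (see Appendix 3) OR". Second limb, sufficient on its own: "Prescription for an antiglycemic medication within 12 months prior to the dapagliflozin dispensing". The row does not say which drug classes count. Insulin appears in the same table's concomitant-medication list as "Insulin (ATC code A10A", and nothing removes it from the second limb.
- **Table 3.4.1-1, off-label row.** One of six alternative criteria is "No diagnostic codes for Type 2 Diabetes Mellitus, at or before the initiation of dapagliflozin use (see definition above". The words are code-only, but the bracket sends the reader back to the either-or row.
- **Synopsis, objectives.** The subgroup is "patients lacking a diagnostic code indicating type 2 diabetes", with no window.
- **Section 1.2, research question 5.** It asks what proportion "does not have a diagnosis of Type II Diabetes during the baseline period or on the index date".
- **Section 2.1.** The subgroup is "patients not reported to have T2DM", with neither source nor window stated.

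**The concern.** Use in patients without T2DM is one of four subgroups named in the primary objective, one of five research questions and one of six off-label criteria. Section 1.1 says the study was requested by regulators, and section 4.1 calls it purely descriptive, so the reported proportion is itself the result. If the protocol's own rules classify the same patient in opposite ways, that proportion depends on which row the programmer follows.

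The possible errors run in different directions. The prescription limb can count an insulin-treated patient without T2DM as T2DM, which understates use outside the indication. A code search limited to 12 months can miss a long-standing diagnosis that was not re-entered, which overstates it. These belong to alternative rules and do not both act on one patient under one rule.

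**Working it through.** **Step 1: apply each rule to the same patients.** The profiles are hypothetical. The last column follows the off-label row's bracketed reference back to the T2DM row.

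| Patient | T2DM row | Research question 5 | Off-label row, literal | Off-label row, via reference |
|---|---|---|---|---|
| A. No T2DM code ever; insulin prescribed 3 months before index | T2DM | counted as undiagnosed | off-label | not off-label |
| B. T2DM coded 3 years before index, not re-entered; no glucose-lowering drug in the past year | not T2DM | counted as undiagnosed | not off-label | off-label |
| C. First T2DM code on the index date; no earlier drug | not T2DM if index date is excluded | not counted | not off-label | off-label if index date is excluded |
| D. No T2DM code and no earlier glucose-lowering drug | not T2DM | counted as undiagnosed | off-label | off-label |

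A, B and C each receive conflicting classifications; only D is treated alike everywhere. For C, the row's label refers to initiation while its criteria look to the time before, so inclusion of the index date is itself unclear. B is realistic under the label quoted in the Introduction, which allows monotherapy "when diet and exercise alone do not provide adequate glycaemic control in patients for whom metformin is considered inappropriate due to intolerance".

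**Step 2: reproduce the plan's only size figure.** Users = T2DM patients × share on oral antidiabetic drugs (OAD) × uptake (Tables 4.2-1 and 4.2-2; EU5 uptake for Belgium), with uptake summed over 2012–2017.

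- France: 65,000 × 0.827 × 17.2% = 9,245.9
- UK: 85,000 × 0.572 × 5.6% = 2,722.7
- Italy: 45,000 × 0.645 × 9.4% = 2,728.4
- Germany: 70,000 × 0.553 × 10.0% = 3,871.0
- Belgium: 15,000 × 0.719 × 10.3% = 1,110.9
- Spain: 18,000 × 0.528 × 6.8% = 646.3

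The sum is about 20,325, as stated. It serves below only as a convenient denominator. It runs to 2017, beyond the 42-month analysis, and the proportions in step 3 do not depend on it.

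**Step 3: how far the rules could diverge.** Let q be the share of users without a T2DM code who had a glucose-lowering prescription in the prior 12 months. Ignoring window differences, the either-or rule leaves (1 − q) of the code-only group. The protocol gives neither q nor the uncoded share, so both are assumed. With 5% uncoded, the code-only rule flags 20,325 × 0.05 = 1,016. The either-or rule then flags:

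| q | Left in group | Share of 1,016 |
|---|---|---|
| 52.8% (lowest country OAD share) | 480 | 47% |
| 63.9% (pooled: 190,399/298,000) | 367 | 36% |
| 82.7% (highest country OAD share) | 176 | 17% |
| 90% | 102 | 10% |
| 95% | 51 | 5% |
| 99% | 10 | 1% |

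The OAD shares are borrowed values: they describe T2DM patients overall, not uncoded dapagliflozin users, and do not count insulin-only treatment. The table shows direction and sensitivity; it is not an estimate.

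**Step 4: the look-back.** Against the median follow-up in section 3.3.1, 12 months is 12/27 = 44% in Germany, 12/36 = 33% in France, 12/44 = 27% in Spain, 12/46 = 26% in Belgium, 12/112 = 11% in Italy and 12/117 = 10% in the UK. These are shares of total recorded time, not of history before index, and not of missed diagnoses. They show that a 12-month and an any-time search differ, and that the difference varies by country.

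**The case against.** The best defence is that the prescription limb is a sensible guard against poor coding. Section 5.1 admits that a GP may enter any diagnosis as the indication for a drug, so a treated T2DM patient may lack a T2DM code. The same section says an indication is mandatory for each prescription, which gives repeated chances to record the diagnosis and weakens the worry about old codes. Twelve months is also the baseline period and the enrolment requirement, so it gives every patient the same look-back; an any-time search does not. Cross-country code harmonisation and analysis detail are left to the SAP. All of this stands. It supports keeping the either-or rule and the 12-month window in view, and it means the absence of a drug-class list is not a defect in itself. It does not settle which of the conflicting rules governs, and section 4.1 has the SAP elaborate the protocol, with major modifications made by amendment.

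Four stronger readings are tempting and are not supported.

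- *The group without T2DM is nearly empty by construction.* The prescription limb reduces the off-label group only if the bracketed reference overrides the row's own words. Even then patients like D remain, and near-emptiness needs q of about 95% or more, which the protocol neither states nor implies.
- *The whole off-label total turns on this rule.* Five of the six criteria (two on age, three on renal function) do not use it.
- *About 10% of users do not have T2DM and none would be detected.* The 90% in section 3.3.2 is a rough assumption about all diabetics, not dapagliflozin users. Non-detection of the insulin-treated also presupposes that the either-or rule governs.
- *A 12-month window discards about 90% of the record.* That fits only the two longest databases.

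**Conclusion.** The contradiction stands on the protocol's wording and needs no outside figure. The definitions differ in evidence (code or prescription; code; diagnosis) and in window (prior 12 months; any time up to initiation; baseline period or index date), and they classify identifiable patients in opposite ways. A named primary subgroup and research question 5 therefore have no single computable answer.

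If the either-or rule governs, the bias is towards understating use outside T2DM. Its size cannot be derived from the document; under the assumed q in the working, the group falls to between 47% and 1% of its code-only size. That insulin counts is the natural reading of an unrestricted term, not an explicit statement. The effect is confined to research question 5, the matching subgroup and one of six off-label criteria. It should be resolved before the first data extraction.

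**What to change.** - State one code-based definition of T2DM with one window, up to and including the index date. Apply it to research question 5, the synopsis and section 2.1 subgroup, and the off-label row. Remove or correct the bracketed reference in that row.
- Report users without a T2DM code in three exclusive groups by prior glucose-lowering prescription: insulin only, other, none. This displays possible under-coding and possible use outside T2DM instead of merging them, and needs no type 1 code list, which Appendix 3 does not contain.
- Show two sensitivity analyses: the code-or-prescription rule, with its drug classes named, and the alternative look-back (12 months versus any time in the record). Fix in advance which look-back is primary.

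The cost is wording in the synopsis, sections 1.2 and 2.1 and Table 3.4.1-1, plus one extra table from data already to be extracted. There are two trade-offs. An any-time look-back differs by country, with median follow-up from 27 to 117 months, so country comparisons on that basis need a caveat. A code-based rule also rests entirely on the T2DM code list, so the Appendix 3 list should be verified before it carries the result.
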